2. STUDY OBJECTIVES AND ENDPOINTS

2.1 Primary Objectives & Endpoints

2.1.1 Objectives:

The co-primary objectives of this study are:

- To evaluate the overall feasibility of using the OncoTreat technology to inform rational selection of off-label FDA-approved or investigational drugs in subjects with advanced pancreatic cancer (PDA) who have progressed on one or two prior lines of systemic therapy. This will include the percentage of subjects who begin an OncoTreat-prioritized agent, defined as having received a single dose of study drug, and the "match rate," defined as the fraction of subjects who match with at least one OncoTreat-prioritized agent (p-value < 1 x 10⁻⁵).
- To evaluate the clinical efficacy of OncoTreat by assessing the objective response rate (ORR) for subjects with advanced PDA treated with OncoTreat-prioritized drugs after disease progression on one or two prior lines of systemic therapy according to Response Evaluation Criteria in Solid Tumors (RECIST) v1.1 criteria.
- 2.1.2 Endpoints:

The co-primary endpoints of interest are:

- The percentage of subjects who begin an OncoTreat-prioritized agent, defined as having received a single dose of study drug, and the "match rate," defined as the fraction of subjects who match with at least one OncoTreat-priotitized agent (p-value $< 1 \ge 10^{-5}$).
- ORR according to RECIST v1.1 criteria.

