10.2 Definitions

Evaluable for toxicity: All patients will be evaluable for toxicity from the time of their first treatment with an OncoTreat-prioritized agent.

Evaluable for objective response: Only those patients who have measurable disease present at baseline, have received at least one cycle of therapy, and have had their disease re-evaluated will be considered evaluable for response. These patients will have their response classified according to the definitions stated below. (*Note*: Patients who exhibit objective disease progression prior to the end of cycle 1 will also be considered evaluable.)

Evaluable for feasibility – primary outcome: All subjects who receive a single dose of study drug will be included in the primary outcome analysis of feasibility.

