12. STATISTICAL CONSIDERATIONS

This is a single arm, phase Ib study with 2 co-primary endpoints:

- Feasibility: The primary objective of this trial is to determine the feasibility of the OncoTreat platform in guiding therapy. The primary outcome is whether a subject begins therapy on Part 2. Previous attempts to match subjects based on DNA profiling have yielded enrollment rates of 3-5% [14, 78]. We hypothesize that we will validate OncoTreat matches for 50% of subjects and that at least 30% of enrolled subjects (60% of matches) will begin therapy on Part 2. With 30 enrolled patients on Part 1, we will have 80% power to detect a treatment rate of 30% on Part 2 compared to a historical treatment rate of 5% with alpha of 0.05. We will also assess the "match rate" the fraction of patients who match with at leaset one drug. With 30 enrolled subjects, we will have 97% power with alpha = 0.05 to detect a 50% match rate (15 of 30 subjects) compared to a (liberal) estimated match rate of 20% based on DNA profiling in PDA.
- Efficacy: The primary clinical efficacy endpoint is the **objective response rate (ORR)** for OncoTreat-prioritized drugs, which corresponds to the number of patients whose tumors demonstrate a 30% or greater reduction from baseline in the sum of the diameters of all target lesions amongst all evaluable patients, as assessed by standard-of-care CT scans. We target estimating the ORR and the corresponding 95% confidence interval.

Secondary endpoints will include: 1) **disease control rate (DCR) at 16 and 24 weeks**, which corresponds to the number of patients whose tumors demonstrate either an objective response or stable disease, defined as a no more than 20% increase from baseline in the sum of the diameters of all target lesions; 2) **median progression-free survival (mPFS)**, defined as the median duration prior to the development of disease progression or patient death; 3) **overall survival (OS)**, defined as time from first dose of OncoType-informed drug to death due to any cause; and 4) **safety and tolerability**, defined as the incidence of Grade 3/4 AEs in terms categorized and graded according to NCI CTCAE v4.0. We will estimate DCR, mPFS, and OS and their 95% confidence interval.

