The phase III trial (NAPOLI-1) that resulted in the FDA-approval of nanoliposomal irinotecan and 5-fluorouracil in the second-line setting demonstrated a median overall survival of 6.1 months versus 4.2 months for 5-fluorouracil monotherapy (primary endpoint), mPFS of 3.1 months, and an ORR of 16% (compared to 1% in the 5-fluorouracil arm) [7]. Fifty-one (12%) patients had not had previous treatment for metastatic disease, 234 (56%) had received one previous line of metastatic treatment, and 132 (32%) had previously received two or more lines of metastatic treatment. The disease control rate was less than 20% and did not differ between treatment groups. Thus, based on historical controls, the ORR for treatment-resistant metastatic PDAC is expected to be no more than 16%.

Using the above mentioned rates, a sample size of n = 9 achieves at least a 80% power to detect a difference of 25% in ORR (30% vs 5%) using a one-sided binomial test with a target alpha of 0.1. To be conservative, we use the minimum number of patients (9) expected to be treated in this calculation. If at the end of the study the total number of objective responses is greater than or equal to 2, we will be able to reject the historical rate of 5% at the significance level of 0.05 with power of 69% and OncoTreat will have demonstrated a clear signal of clinically meaningful improvement in the primary endpoint for patients with advanced, previously-treated PDA. Assuming about 30% of enrolled patients will receive an OncoTreat-informed treatment, N = 30 subjects is an appropriate sample size for this prospective study.

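### Section 10.2 defines the feasibility analysis set by the success event itself, in conflict with the 30 enrolled subjects used elsewhere

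*Combined protocol and SAP*

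**What the plan says.** Section 10.2 has three entries on who is evaluable: for toxicity, for objective response, and for the primary feasibility outcome. The feasibility entry consists of one sentence: "All subjects who receive a single dose of study drug will be included in the primary outcome analysis of feasibility". The response entry is worded as a restriction and begins "Only those patients who have measurable disease present at baseline".

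Section 2.1.2 gives the feasibility endpoint as "the percentage of subjects who begin an OncoTreat-prioritized agent, defined as having received a single dose of study drug", together with the match rate. It does not name a denominator for the treatment rate. Objective 2.1.1 describes the population as subjects "who have progressed on one or two prior lines of systemic therapy", although Section 1.1 has Part 1 enrolling newly diagnosed subjects.

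Section 12 works from enrolled subjects. Its hypothesis is that "at least 30% of enrolled subjects (60% of matches) will begin therapy on Part 2", and its power statement reads "With 30 enrolled patients on Part 1, we will have 80% power to detect a treatment rate of 30% on Part 2". The match rate is planned as 15 of 30. The sample-size paragraph ends on the same base: "Assuming about 30% of enrolled patients will receive an OncoTreat-informed treatment". The synopsis also uses 30 enrolled, and Section 5.4 says thirty subjects are needed for the primary endpoint. Section 4.2 keeps 30 enrolled on Part 1 apart from a maximum of 30 treated on Part 2.

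**The concern.** Being in the 10.2 set and being a success are the same event. A rate computed within that set is therefore fixed at 100% whatever happens in the trial.

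The treatment rate is meant to show what share of enrolled patients can be started on a matched drug. The subjects who count against feasibility are those never dosed. Section 4.1 foresees them: if no agent is identified or available by the second progression, the subject is recorded as a screen failure for Part 2. A literal use of 10.2 removes all such subjects from a co-primary analysis. If the sentence is taken to cover the match rate as well, that rate has the same problem, because a subject dosed with a prioritized agent has already been matched.

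The 10.2 sentence is the only evaluability rule stated for this outcome, so an analyst who builds analysis sets from Section 10 would start from it.

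**Working it through.** **Inputs**

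- Enrolled on Part 1: 30 (Sections 4.2 and 12)
- Expected match rate: 50% (Section 12)
- Expected share of matches treated: 60% (Section 12)
- Target and historical treatment rates: 30% and 5%, alpha 0.05 (Section 12 and synopsis)
- Success event: a single dose of study drug (Section 2.1.2)
- Set named in Section 10.2: subjects with a single dose

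**Step 1. The plan's own count.** 30 × 0.50 = 15 matched, and 15 × 0.60 = 9 treated. Then 9/30 = 30%, which is the Section 12 target, and 9 is the number the ORR calculation uses. The planned 30% therefore has 30 enrolled as its denominator.

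**Step 2. The plan's own power.** The documents state neither the feasibility test nor its sidedness. With n = 30, a two-sided normal approximation with the variance taken at 30% has standard error √(0.30 × 0.70/30) = 0.0837.

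- Without continuity correction: 0.25/0.0837 − 1.96 = 1.03, power 84.8%. The synopsis says 84%.
- With continuity correction 1/(2 × 30) = 0.0167: (0.25 − 0.0167)/0.0837 − 1.96 = 0.83, power 79.6%. Section 12 says 80%.

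Both stated figures can thus be approximated with 30 enrolled subjects as the sample. This supports 30 as the intended base; it does not prove which test was meant. The exact one-sided binomial test, rejecting at 5 or more of 30, has type I error 0.0156 and power 97.0%, and matches neither figure. The 80% against 84% discrepancy is a separate matter.

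**Step 3. The two denominators side by side.** The intervals are Clopper-Pearson: lower limit = 2.5% point of Beta(k, n − k + 1), upper limit = 97.5% point of Beta(k + 1, n − k).

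| Treated, k | Rate on 30 enrolled (exact 95% CI) | Rate on the literal 10.2 set | Subjects left out by 10.2 |
|---|---|---|---|
| 9 (planned) | 9/30 = 30.0% (14.7% to 49.4%) | 9/9 = 100% | 30 − 9 = 21 (70%) |
| 2 | 2/30 = 6.7% (0.8% to 22.1%) | 2/2 = 100% | 30 − 2 = 28 (93%) |

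The second row is close to the historical rate, since 30 × 0.05 = 1.5 subjects. On 30 enrolled the two rows differ clearly. On the literal 10.2 set they are identical, so that set cannot separate a feasible platform from an infeasible one.

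**The case against.** The best reply is that 10.2 excludes nobody. It says dosed subjects are included, whereas the response entry in the same section begins with the word Only, so the authors knew how to restrict when they meant to. Section 4.1 places Part 2 consent and a required biopsy before the first dose, so a subject can enter Part 2 and never be treated. On that reading 10.2 is a numerator rule: one dose is enough to count as started, in contrast to the full cycle plus re-evaluation asked for under response.

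Section 12 also settles the denominator in practice. A yes/no outcome compared with a 5% historical rate makes sense only if undosed subjects are counted, and Section 1.1 speaks of 30 evaluable patients. Part 1 is a separate protocol that is not among these documents, so how it treats undosed subjects cannot be checked.

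Much of this stands. It makes 30 enrolled the likely intention and keeps the practical risk low to moderate. It does not remove the conflict. The neighbouring 10.2 entries define who enters each analysis, so this entry reads naturally in the same way; nothing labels it a numerator rule; and no text says that Section 12 prevails or that undosed subjects are non-successes. Section 1.1 is a description of the trial and does not define an analysis set.

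**Conclusion.** The concern holds, as a minor point. The one sentence that says who is evaluable for feasibility names the subjects who have already succeeded, and it conflicts with the 30 enrolled subjects behind the hypothesis, the power and the expected 9 treated. If followed literally, it reports 100% in place of 30.0% at the planned count and drops 21 of 30 subjects.

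These figures illustrate the literal reading and do not forecast what the analysts will do. The documents do not propose testing k/k, so no inflation of the error rate is claimed. The conclusion rests on reading 10.2 as an analysis-set rule, as its heading and neighbouring entries suggest. If it was meant as a numerator rule, the fault is ambiguous wording and the same correction applies. The planned analysis is not missing and the sample size is not affected.

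**What to change.** Replace the feasibility entry in Section 10.2 with wording such as: *Evaluable for feasibility: all subjects enrolled on Part 1 (n = 30). A subject who receives at least one dose of an OncoTreat-prioritized agent on Part 2 is a success; every other enrolled subject is a non-success.*

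In Section 2.1.2, state that the treatment rate and the match rate both use these 30 subjects. Because objective 2.1.1 speaks of subjects who have progressed while Part 1 enrolls newly diagnosed ones, add that an enrolled subject who never reaches Part 2, for any reason, stays in the 30, as the Section 12 count implies.

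The cost is a short rewrite of one entry in 10.2 and one or two clauses in 2.1.2. It needs no new data and no change in sample size or conduct, since it restates the plan's own 30 × 50% × 60% = 9.

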10.3 Disease Parameters

Measurable disease: Measurable lesions are defined as those that can be accurately measured in at least one dimension (longest diameter to be recorded for non-nodal lesions and short axis for nodal lesions) as ≥ 20 mm by chest x-ray, as ≥ 10 mm with CT scan, or ≥ 10 mm with calipers by clinical exam. All tumor measurements must be recorded in millimeters (or decimal fractions of centimeters).

Note: Tumor lesions that are situated in a previously irradiated area might or might not be considered measurable. If the investigator thinks it appropriate to include them, the conditions under which such lesions should be considered must be defined in the protocol.

Malignant lymph nodes: To be considered pathologically enlarged and measurable, a lymph node must be ≥ 15 mm in short axis when assessed by CT scan (CT scan slice thickness
recommended to be no greater than 5 mm). At baseline and in follow-up, only the short axis will be measured and followed.

Non-measurable disease: All other lesions (or sites of disease), including small lesions (longest diameter <10 mm or pathological lymph nodes with \geq 10 to <15 mm short axis), are considered non-measurable disease. Bone lesions, leptomeningeal disease, ascites, pleural/pericardial effusions, lymphangitis cutis/pulmonitis, inflammatory breast disease, and abdominal masses (not followed by CT or MRI), are considered as non-measurable.

Note: Cystic lesions that meet the criteria for radiographically defined simple cysts should not be considered as malignant lesions (neither measurable nor non-measurable) since they are, by definition, simple cysts. Cystic lesions thought to represent cystic metastases can be considered as measurable lesions, if they meet the definition of measurability described above. However, if non-cystic lesions are present in the same patient, these are preferred for selection as target lesions.

Target lesions: All measurable lesions up to a maximum of 2 lesions per organ and 5 lesions in total, representative of all involved organs, should be identified as target lesions and recorded and measured at baseline. Target lesions should be selected on the basis of their size (lesions with the longest diameter), be representative of all involved organs, but in addition should be those that lend themselves to reproducible repeated measurements. It may be the case that, on occasion, the largest lesion does not lend itself to reproducible measurement in which circumstance the next largest lesion which can be measured reproducibly should be selected. A sum of the diameters (longest for non-nodal lesions, short axis for nodal lesions) for all target lesions will be calculated and reported as the baseline sum diameters. If lymph nodes are to be included in the sum, then only the short axis is added into the sum. The baseline sum diameters will be used as reference to further characterize any objective tumor regression in the measurable dimension of the disease.

Non-target lesions: All other lesions (or sites of disease) including any measurable lesions over and above the 5 target lesions should be identified as non-target lesions and should also be recorded at baseline. Measurements of these lesions are not required, but the presence, absence, or in rare cases unequivocal progression of each should be noted throughout follow-up.

10.4 Methods for Evaluation of Measurable Disease

All measurements should be taken and recorded in metric notation using a ruler or calipers. All baseline evaluations should be performed as closely as possible to the beginning of treatment and never more than 4 weeks before the beginning of the treatment.

The same method of assessment and the same technique should be used to characterize each identified and reported lesion at baseline and during follow-up. Imaging-based evaluation is preferred to evaluation by clinical examination unless the lesion(s) being followed cannot be imaged but are assessable by clinical exam.

Conventional CT and MRI: This guideline has defined measurability of lesions on CT scan based on the assumption that CT slice thickness is 5 mm or less. If CT scans have slice thickness greater than 5 mm, the minimum size for a measurable lesion should be twice the slice thickness. MRI is also acceptable in certain situations (e.g., for body scans).

Use of MRI remains a complex issue. MRI has excellent contrast, spatial, and temporal resolution; however, there are many image acquisition variables involved in MRI, which greatly impact image quality, lesion conspicuity, and measurement. Furthermore, the availability of MRI is variable globally. As with CT, if an MRI is performed, the technical specifications of the scanning sequences used should be optimized for the evaluation of the type and site of disease. Furthermore, as with CT, the modality used at follow-up should be the same as was used at baseline and the lesions should be measured/assessed on the same pulse sequence. It is beyond the scope of the RECIST guidelines to prescribe specific MRI pulse sequence parameters for all scanners, body parts, and diseases. Ideally, the same type of scanner should be used and the image acquisition protocol should be followed as closely as possible to prior scans. Body scans should be performed with breath-hold scanning techniques, if possible.

Tumor markers: Tumor markers alone cannot be used to assess response. If markers are initially above the upper normal limit, they must normalize for a patient to be considered in complete clinical response.

10.5 Response Criteria – RECIST Criteria 10.5.1 Evaluation of Target Lesions

Complete Response (CR): Disappearance of all target lesions. Any pathological lymph nodes (whether target or non-target) must have reduction in short axis to <10 mm.

Partial Response (PR): At least a 30% decrease in the sum of the diameters of target lesions, taking as reference the baseline sum diameters.

Progressive Disease (PD): At least a 20% increase in the sum of the diameters of target lesions, taking as reference the smallest sum on study (this includes the baseline sum if that is the smallest on study). In addition to the relative increase of 20%, the sum must also demonstrate an absolute increase of at least 5 mm. (*Note*: the appearance of one or more new lesions is also considered progressions).

Stable Disease (SD): Neither sufficient shrinkage to qualify for PR nor sufficient increase to qualify for PD, taking as reference the smallest sum diameters while on study.

10.5.2 Evaluation of Non-Target Lesions

Complete Response (CR): Disappearance of all non-target lesions and normalization of tumor marker level. All lymph nodes must be non-pathological in size (< 10 mm short axis).

Note: If tumor markers are initially above the upper normal limit, they must normalize for a patient to be considered in complete clinical response.

Non-CR/Non-PD: Persistence of one or more non-target lesion(s) and/or maintenance of tumor marker level above the normal limits.

Progressive Disease (PD): Appearance of one or more new lesions and/or unequivocal progression of existing non-target lesions. Unequivocal progression should not normally trump target lesion status. It must be representative of overall disease status change, not a single lesion increase. Although a clear progression of "non-target" lesions only is exceptional, the opinion of the treating physician should prevail in such circumstances, and the progression status should be confirmed at a later time by the review panel (or Principal Investigator).

10.5.3 Evaluation of Best Overall Response

The best overall response is the best response recorded from the start of the treatment until disease progression/recurrence (taking as reference for progressive disease the smallest measurements recorded since the treatment started). The patient's best response assignment will depend on the achievement of both measurement and confirmation criteria.

Target Lesions	Non-Target Lesions	New Lesions	Overall Response	Best Overall Response when Confirmation is Required*
CR	CR	No	CR	≥ 4 wks.
				Confirmation**
CR	Non-CR/Non-PD	No	PR	
CR	Not evaluated	No	PR	\geq 4 wks.
PR	Non-CR/Non-	No	PR	Confirmation**
	PD/not evaluated			
SD	Non-CR/Non-	No	SD	documented at least
	PD/not evaluated			once \geq 4 wks. from
				baseline**
PD	Any	Yes or	PD	
		No		
Any	PD***	Yes or	PD	no prior SD, PR or CR
		No		
Any	Any	Yes	PD	

Table 10Disease Assessment For Patients with Measurable Disease

* See RECIST 1.1 manuscript for further details on what is evidence of a new lesion.
 ** Only for non-randomized trials with response as primary endpoint.

*** In exceptional circumstances, unequivocal progression in non-target lesions may be accepted as disease progression.

Note: Patients with a global deterioration of health status requiring discontinuation of treatment without objective evidence of disease progression at that time should be reported as "symptomatic deterioration." Every effort should be made to document the objective progression even after discontinuation of treatment.

10.6 Duration of Response

Duration of overall response: The duration of overall response is measured from the time measurement criteria are met for CR or PR (whichever is first recorded) until the first date that recurrent or progressive disease is objectively documented (taking as reference for progressive disease the smallest measurements recorded since the treatment started).

The duration of overall CR is measured from the time measurement criteria are first met for CR until the first date that progressive disease is objectively documented.

Duration of stable disease: Stable disease is measured from the start of the treatment until the criteria for progression are met, taking as reference the smallest measurements recorded since the treatment started, including the baseline measurements.

10.7 Analysis of Endpoints

Efficacy and safety endpoints that will be evaluated are listed below:

Efficacy

